4.2 Discussion of Study Design

This trial is designed to pre-screen subjects via a flortaucipir scan, who have objectively verified cognitive impairment and etiology diagnosed or suspected to be Alzheimer's disease, and have indicated their interest in participating in Lilly sponsored trials that require tau imaging for inclusion.

4.3 Method of Assignment of Subjects to Treatment Groups

Flortaucipir F 18:

All subjects will receive a single IV bolus administration target dose of 370 MBq (10 mCi) of flortaucipir F 18 Injection.

4.4 Blinding

A blinded design is not used for this trial, because all subjects will receive the same medication.

4.5 Determination of Sample Size

This is a pre-screening study that targets subjects who are interested in participating in AD therapeutic clinical trials and have expressed a preliminary interest in a trial like the LMDC trial. Therefore, approximately 500 subjects will be enrolled in this study.

5 CHANGES IN THE CONDUCT OF THE STUDY OR PLANNED ANALYSES

5.1 Changes in the Conduct of the Study

There were no changes in the conduct of the study at the time of preparing this statistical analysis plan.

5.2 Changes from the Analyses Planned in the Protocol/CIP

There were no changes in the analyses planned in the Protocol/CIP at the time of preparing this statistical analysis plan.

6 BASELINE, EFFICACY AND SAFETY EVALUATIONS

6.1 Schedule of Evaluations

Evaluations/Procedures	Screening Visit ^a	Flortaucipir F 18 Imaging Visit	End of Flortaucipir F 18 Imaging (prior to discharge)	Follow-up Phone Call
Signed Consent	X			
Demographics	X			
Medical History/Neurologic Disease History	X			
Concomitant Meds	X	X		
Vital Signs ^b	X			
ECG	X			
MMSE and CBB ^c	X			
Serum beta-hCG ^d	X			
Urine Pregnancy Test ^e		X		
flortaucipir F 18 scan		X		
Evaluation by a physician ^f	X	X	X	
Adverse Events	X	X	X	X
Serious Adverse Events	X	X	X	X

- a. Screening may take place over several days. All assessments must be performed within approximately 30 days of the ¹⁸F-AV-1451 imaging session.
- b. Vital signs (pulse, respiratory rate, supine blood pressure). Weight will be taken at the imaging visit.
- c. All patients will complete the MMSE, performed using Serial-7's, followed by the CBB.
- d. Serum beta-hCG pregnancy test at screening for females of childbearing potential.
- e. For women of childbearing potential, a negative urine pregnancy test must be obtained within 24 hours prior to the flortaucipir F 18 injection.
- f. A physician must see the patient during screening. For the imaging visit, a physician or PI designee may evaluate the patient.

6.2 Time Point Algorithms

6.2.1 Relative Day

The date of first dose of study drug (flortaucipir F 18) will be considered relative day 1, and the day before the first dose of study drug will be relative day -1. Relative days will be calculated as follows only when the full assessment date is known (i.e., partial dates will have missing relative days):

For days on or after the first dose of study drug:

Date of Assessment – Date of First Dose of Study Drug + 1.

For days before the first dose of study drug:

Date of Assessment – Date of First Dose of Study Drug.

6.2.2 Windows

No window algorithm is being used for this study.

6.3 Screening Assessments

Screening may take place over several days. All screening assessments will be performed within 30 days prior to flortaucipir F 18 injection. Screening assessments will include:

- Informed consent for subject;
- Demographics (age, birth gender, years of education, race, ethnicity); weight/height; weight will be collected during the imaging visit.
- Medical history, concomitant medications;
- Vital Signs (pulse, respiration rate, supine blood pressure)
- An ECG will be performed to assess the subject's cardiac status. If an ECG was performed within the last 12 months of the flortaucipir (¹⁸F) PET Imaging Visit and is available for review, the ECG does not need to be repeated.
- ApoE status, if available;
- Disease history (date/months since symptom onset, date/months since diagnosis, family history of relevant neurologic disease);
- Cognitive status interview, including MMSE, performed using Serial-7's and CBB;
- A physician will see the subject during the screening visit.
- For women of childbearing potential, a negative serum pregnancy test must be obtained at the screening visit

Weight will be displayed in kilograms (kg), height will be displayed in centimeters (cm). Weights and heights recorded in alternate units will be converted to the units being displayed using standard conversion formulas. Body mass index (BMI) will be calculated as weight (kg) divided by height squared (cm²).

APOE4 Positive is any subject with at least one of their two APOE alleles as an E4 allele.

Each subject's age (years) will be calculated as the difference of the year of his/her informed consent date and the year of his/her birth.

The MMSE (Folstein et al., 1975) is a brief instrument used to assess cognitive function in elderly subjects. The instrument is divided into 2 sections. The first section measures orientation, memory, and attention. The maximum score for the first section is 21. The second section tests the ability of the subject to name objects, follow verbal and written commands, write a sentence, and copy figures. The maximum score for the second section is 9. The range for the total MMSE score is 0 to 30, the sum of each correct answer, with higher scores indicating better cognition.

The CBB will be administered to patients at screening in addition to the MMSE. The CBB is a brief (15-18 minute), computer-based cognitive test battery designed to measure psychomotor function, attention, working memory and memory (Maruff et al. 2009, 2013; Fredrickson et al. 2010; Darby et al. 2012). The CBB has been shown to be sensitive to AD-related cognitive decline in healthy older adults and in adults with amnestic MCI (Darby et al. 2002, 2012; Lim et al. 2013a, b) as well as to improvement in cognition arising from treatment with cognitive enhancing drugs (Davison et al. 2011; Jaeger et al. 2011; Nathan et al. 2013). The CBB will be administered at screening in an effort to further characterize patients enrolled in the study.

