1 LIST OF ABBREVIATIONS AND DEFINITIONS OF TERMS

Table 1: Abbreviations and Definitions of Terms

A β	amyloid- β
AD	Alzheimer's disease
AE	adverse event
ATC	Anatomical therapeutic chemical classification
BMI	body mass index
CBB	CogState Brief Battery
CIP	Clinical investigational plan
cm	centimeters
CRO	contract research organization
DBP	diastolic blood pressure
ECG	electrocardiogram
eCRF	electronic case report form
IND	investigational new drug
IV	Intravenous
K _d	dissociation constant
kg	Kilograms
max	Maximum
MBq	Megabecquerel
mCi	Millicuries
MCI	mild cognitive impairment
MedDRA	Medical Dictionary for Regulatory Activities
min	Minimum
MMSE	Mini-Mental State Examination
mSv	Millisievert
MUBADA	Multiblock barycentric discriminant analysis
n	number of subjects
nM	Nanomolar
PET	positron emission tomography
SAE	Serious adverse event
SBP	systolic blood pressure
SD	standard deviation
SOC	system organ class
SOP	standard operating procedure
SUV _r	standardized uptake value ratio
TEAE	treatment-emergent adverse event
WHO	World Health Organization

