7 STATISTICAL METHODS

7.1 General Methodology

All values will be summarized as a single group, early symptomatic AD. Frequency distributions including counts and percentages will be reported for all categorical outcomes. Summary statistics including number of subjects [N], mean, standard deviation [SD], median, quartiles, minimum and maximum values will be presented for all continuous outcomes.

All statistical analyses will be performed using SAS® version 9.3 or higher. Patient listings of all data from the eCRF as well as any derived variables will be presented.

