8.3 Demographic and Other Baseline Characteristics

All baseline summaries will be based on the safety population.

Frequency distributions and summary statistics for demographic and baseline variables will be presented across all subjects. Key demographic and baseline characteristics to be summarized include: age, birth gender, race, ethnicity, height, weight, BMI, highest level of education, alcohol history, recreational drug use history, smoking history, MMSE, CBB (if the CBB assessment is repeated, this second CBB score will be used in the CBB summary table), and ApoE Genetic testing.

All demographic and baseline characteristics data will be presented in listings.

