8.10.1.1 Unit Conversion and Volume Calculation

All exposure tables will display volume in MBq. Radioactive dose collected in millicuries (mCi) will be converted to MBq as follows:

$$MBq = 37 \times mCi$$

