9 COMPUTER SOFTWARE

All analyses will be performed by Chiltern using SAS® Version 9.3 or later. All summary tables and data listings will be prepared utilizing SAS® software.

The standard operating procedures (SOPs) of Chiltern will be followed in the creation and quality control of all data displays and analyses.

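### SAP 6.3 computes BMI from height in centimetres without converting to metres, so every value is 10,000 times below the kg/m² scale

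*SAP*

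**What the plan says.** SAP section 6.3 first fixes the units: "Weight will be displayed in kilograms (kg), height will be displayed in centimeters (cm"). It then deals with values collected in other units: "Weights and heights recorded in alternate units will be converted to the units being displayed using standard conversion formulas". The next sentence is the derivation: "Body mass index (BMI) will be calculated as weight (kg) divided by height squared (cm²").

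BMI appears in two other places in the SAP. The abbreviation list in section 1 expands it as "body mass index", with no unit or formula. Section 8.3 includes it among the key baseline variables ("age, birth gender, race, ethnicity, height, weight, BMI" and others), again without a unit. Section 7.1 adds that "Patient listings of all data from the eCRF as well as any derived variables will be presented", so BMI will be listed subject by subject as well as summarised. The protocol does not mention BMI.

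**The concern.** BMI is conventionally expressed in kg/m². The three sentences of section 6.3, read together, bring every height to centimetres and then divide kilograms by square centimetres. Nothing between the data and the formula takes height to metres, and there is no multiplying constant to make up for it. A programmer who follows the text produces numbers that are not BMI on its usual scale.

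A table or listing would be at stake, not an inference. The study is purely descriptive, so the baseline summary is part of its planned output, and BMI is a named item in it. If the rule were coded literally, the summary and the listing would both be wrong. If a programmer silently corrected it, the program and the SAP would disagree.

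**Working it through.** **Inputs**
- Weight in kg, height in cm, formula weight/height² with height in cm: SAP 6.3.
- Comparison scale kg/m²: the standard definition of BMI. The documents do not state it.
- Example weights and heights: assumed, because the documents give no subject values and no numerical BMI to reproduce.

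**Scale factor**

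With weight *w* in kg and height *h* in cm:
- as written: *w* / *h*²
- standard: *w* / (*h*/100)² = 100² × *w* / *h*² = 10,000 × *w* / *h*²

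The ratio is 10,000 whatever the weight or height.

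**Assumed examples**

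| Weight (kg) | Height (cm) | As written (kg/cm²) | Standard (kg/m²) |
|---|---|---|---|
| 45 | 150 | 45/150² = 0.0020 | 45/1.50² = 20.0 |
| 75 | 170 | 75/170² = 0.0026 | 75/1.70² = 25.95 |
| 120 | 190 | 120/190² = 0.0033 | 120/1.90² = 33.24 |

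Over an assumed range of 40 to 150 kg and 140 to 200 cm:
- smallest: 40/200² = 0.0010, which is 10.0 kg/m²
- largest: 150/140² = 0.0077, which is 76.5 kg/m²

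**Effect on the summary statistics**

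The factor is constant, so the mean, SD, median, quartiles, minimum and maximum planned in SAP 7.1 all shrink by the same 10,000. Before rounding, nothing is lost and multiplying back restores every figure.

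Rounding could lose information. The documents do not state a display precision, so this part is conditional:
- At one decimal, every value in the assumed range prints as 0.0.
- At two decimals, every value prints as 0.00 or 0.01.
- At three decimals, a printed 0.003 covers 0.0025 to 0.0035, that is 25 to 35 kg/m².
- A difference of 0.1 kg/m² is 0.1/10,000 = 0.00001 on the written scale, so five decimals would be needed to show it.

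**Is the formula corrected elsewhere?**

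No. Sections 1 and 8.3 only name BMI. Neither document contains kg/m², a division of height by 100, or a factor of 10,000. A PDF reading error is unlikely, because cm² agrees with the preceding sentence, which sets height in centimetres.

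**The case against.** The strongest reply is that this is a slip in a unit label. Every programmer knows how BMI is defined, a baseline BMI of 0.003 is implausible on sight, and SAP section 9 says that the contractor's standard procedures "will be followed in the creation and quality control of all data displays and analyses". Height and weight are listed too, so any reader could recompute the value. BMI is not an eligibility criterion, defines no population and enters no imaging or safety analysis. The SAP plans no covariate adjustment for the primary analyses and no subgroup analyses, and neither study objective depends on BMI.

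Most of this stands, and it is why the point ranks as minor. Two things limit it. Quality control ordinarily checks output against the specification, and here the specification carries the error. And relying on the programmer to depart from the text leaves the SAP describing a calculation that was not done.

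It could also be said that section 6.3 leaves conversions to standard formulas, so that a step to metres is implied. That sentence covers only conversion into the displayed units, which for height is centimetres. The dose conversion written out in section 8.10.1.1 ("Radioactive dose collected in millicuries (mCi) will be converted to MBq as follows") does not settle the matter either way: one explicit factor does not establish a general practice, and the BMI point does not rest on it.

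**Conclusion.** The BMI rule in SAP 6.3 is wrong as written. It gives values exactly 10,000 times below kg/m² for every subject, and no other text corrects it. The conclusion rests on the SAP's own wording and the standard definition of BMI. The example weights and heights are assumed, but the factor does not depend on them. The rounding consequences depend on a display precision that the documents do not give.

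Severity is minor: the error is confined to one descriptive baseline variable and its listing, is easy to see, and can be reversed from listed height and weight.

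**What to change.** Replace the BMI sentence in SAP 6.3 with: *BMI (kg/m²) = weight (kg) / [height (cm)/100]²*. Show kg/m² as the unit in the baseline table of section 8.3 and in the corresponding listing, and check that the program line matches.

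The cost is one line of SAP text, one line of code and a unit label. No new data are needed, and no other analysis or aspect of study conduct changes.

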5.3 Selection of Subjects

5.3.1 Inclusion Criteria

Patients must meet the following criteria to enroll in this study:

1. Men or women, at least 60 to 85 years of age at the time of consent;
2. Patients with gradual and progressive change in memory function reported by the patient or informant for ≥ 6 months;
3. Patients who have a MMSE score between 20-28 inclusive; performed using Serial-7's.
4. Patients who are willing to undergo a PET scan using flortaucipir F 18;
5. Patients who give informed consent or have a legally authorized representative (LAR) available to consent at the time of enrollment; and
6. A study partner who must be available if the patient enters the treatment trial.

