7. PROCEDURES AND METHODS

7.1. Assessment Periods

See [Section 11.2](#), Study Flow Charts.

7.1.1. Screening Visit:

Screening may take place over several days. All screening assessments will be performed within approximately 30 days prior to flortaucipir F 18 injection.

Screening assessments will include:

- Informed consent for patient;
- Demographics (age, gender, years of education, race, ethnicity); weight/height; Weight will be collected during the imaging visit.
- Medical history, concomitant medications;
- Vital Signs (pulse, respiration rate, supine blood pressure)
- An ECG will be performed to assess the participant's cardiac status. If an ECG was performed within the last 12 months of the flortaucipir (¹⁸F) PET Imaging Visit and is available for review, the ECG does not need to be repeated.
- ApoE status, if available;
- Disease history (date/months since symptom onset, date/months since diagnosis, family history of relevant neurologic disease);
- Cognitive status interview, including MMSE, performed using Serial-7's and CBB;
- A physician will see the patient during the screening visit.
 - Note: A physician will see the patient during the screening visit. However individual screening assessments may be delegated to a designee by the PI.
- For women of childbearing potential, a negative serum pregnancy test must be obtained at the screening visit.

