7.2 Adjustments for Covariates

Not applicable for the primary analyses.

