7.8 Examination of Subgroups

No subgroup analysis will be performed.

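### SAP 6.3 derives age by subtracting calendar years, so tabulated age can be one year above completed age at consent, the basis of the entry criterion (minor, descriptive output only)

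*SAP*

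**What the plan says.** SAP 6.3 (Screening Assessments) gives the only age derivation in either document: "age (years) will be calculated as the difference of the year of his/her informed consent date and the year of his/her birth". It makes no correction for whether the birthday has passed.

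Protocol 5.3.1, criterion 1, admits "Men or women, at least 60 to 85 years of age at the time of consent".

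SAP 8.3 puts age first among the baseline variables: "Key demographic and baseline characteristics to be summarized include: age, birth gender, race, ethnicity, height, weight, BMI". It also calls for listings of all demographic data. Under SAP 7.1, continuous variables are reported with mean, SD, median, quartiles, minimum and maximum.

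Age has no inferential role. On covariate adjustment SAP 7.2 says "Not applicable for the primary analyses", and SAP 7.8 says "No subgroup analysis will be performed".

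Neither document says whether the database holds full birth date or birth year only. Protocol 7.1.1 lists "Demographics (age, gender, years of education, race, ethnicity" among the screening items, but does not say whether age is a field entered by the site.

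**The concern.** A limit of 60 to 85 years is ordinarily read as completed years, that is, age at last birthday. A difference of calendar years equals completed years only when the birthday falls on or before the consent date. Otherwise it is exactly one year higher, and it is never lower. The table would therefore report age on a basis different from the one used to admit subjects, with no note to say so.

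At stake is how well the baseline table and listing describe the sample. A maximum age of 86 in a study capped at 85 would invite a query with no real violation behind it. Reported age would also depend partly on the time of year at which subjects consented.

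**Working it through.** The documents state no age result, so there is no figure to reproduce. The check compares the SAP rule with completed years.

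**Inputs.** The age rule is from SAP 6.3, the entry range from Protocol 5.3.1, and the planned size from SAP 4.5 ("approximately 500 subjects will be enrolled in this study"). Uniform birthdays and uniform consent dates are assumptions; neither document gives data on them.

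**Formulas.**
- SAP age = consent year − birth year.
- Completed age = consent year − birth year − 1 if the consent month/day precedes the birth month/day; otherwise the year difference alone.

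**Worked cases, illustrative consent on 1 June 2018.**

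| Born | SAP age | Completed age | Effect |
|---|---|---|---|
| 1 Dec 1932 | 86 | 85 | Eligible, shown above the limit |
| 1 Dec 1933 | 85 | 84 | Overstated, still in range |
| 1 Dec 1957 | 61 | 60 | Overstated, still in range |
| 1 Dec 1958 | 60 | 59 | Ineligible, shown in range |
| 1 Mar 1932 | 86 | 86 | Rules agree |

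**Share overstated.** For consent on day d of a 365-day year with uniform birthdays, the share is (365 − d)/365.
- 1 March (d = 60): 305/365 = 84%.
- 1 July (d = 182): 183/365 = 50%.
- 1 December (d = 335): 30/365 = 8%.
- Averaged over all consent days: 182/365 = 49.9%, and 0.499 × 500 ≈ 249.

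Each affected subject is one year high, so the mean is about 0.5 year above mean age at last birthday.

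**Eligible subjects shown as 86.** The count is 500 × share aged 85 × 0.499. The age distribution is assumed, on completed ages 60 to 85:
- normal, mean 73, SD 6: share 0.0093, about 2 subjects;
- normal, mean 75, SD 7: share 0.0223, about 6 subjects;
- uniform: share 1/26 = 0.0385, about 10 subjects.

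**Against exact decimal age.** Write birth and consent as fractions of the year, uniform and independent.
- The SAP rule's error is birth fraction − consent fraction. It lies between −1 and +1, with mean 0 and SD √(1/12 + 1/12) = 1/√6 = 0.41 year.
- The completed-years error is uniform between −1 and 0, with mean −0.5 and root mean square 1/√3 = 0.58 year.

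**The case against.** The strongest reply is that nothing depends on this variable. The study is a single descriptive group, and age is neither a covariate nor a subgroup factor. That stands, and it fixes the point as minor.

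A second reply is that the SAP rule is closer to exact age than completed years are: mean error 0 against −0.5 year, and root mean square 0.41 against 0.58. That also stands. The case for completed years is agreement with the entry criterion, not greater accuracy against decimal age.

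A third reply is that the database may hold only birth year, which would explain the rule. The documents do not settle this. The word age in the screening list does not establish a separate site-entered field: SAP 6.3 has the same list shortly before the sentence that derives age. Any fix is therefore conditional.

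A reader might infer more than the documents support:
- **That reported age generally fails to match 60 to 85.** A subject aged 60 to 84 stays in range even when overstated.
- **That quartiles conflict with eligibility.** They can shift upward, but a shifted quartile does not contradict the age limits.
- **That violations would go undetected.** A 59-year-old enrolled in error would be shown as 60, but no section judges eligibility from derived age. Protocol 10.3 requires deviations to be documented and reported, and Protocol 10.6 has a monitor verify eCRF entries against source.
- **That analysis sets or imaging results would move.** Protocol 8.1.1 refers to eligible patients in its safety population, and SAP 8.9.1 and 8.9.2 split imaging summaries by eligibility. Neither document ties that eligibility to the derived age, and the safety population in SAP 8.1.2 has no age condition.

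**Conclusion.** The point holds as a minor correction. The SAP's age variable is not on the same basis as the entry criterion, and no other section reconciles them. Subjects with a birthday after the consent date are tabulated one year above completed age. The estimate of about half the sample rests on uniform birthdays and consent dates; for a single consent date the share runs from 84% on 1 March to 8% on 1 December.

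The consequence is confined to the age summary and listing. The visible conflict among eligible subjects is 85 shown as 86, for roughly 2 to 10 of 500 under the age distributions tried. The documents give no basis for saying that enrolment, imaging findings or safety results would change.

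**What to change.** Amend SAP 6.3 according to what the database holds.

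- **Full birth date held:** define age as completed years at informed consent, that is, the year difference, minus 1 if the consent month/day precedes the birth month/day. This costs one sentence and one derivation line, with no new data.
- **Birth year only, with a site-recorded age at consent on the eCRF:** report the recorded age. This costs one sentence.
- **Birth year only, with no recorded age:** keep the rule, footnote the table and listing to say that tabulated age may exceed completed age by 1 year, and take age eligibility from site records. This costs a footnote and a cross-reference.

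The sponsor should confirm which case applies before the tables are produced.
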